3.6. Concomitant Therapy

3.6.1. Prior Treatments

Any prior therapy including but not limited to treatment for COVID -19 within 30 days prior to signing informed consent will be recorded.

Prior therapy information should include:

- Drug Name;
- Reason for use;
- Dates of administration including start and end dates;
- Dosage information including administration route, dose and frequency.

Prior therapy with antivirals including Remdesivir® or other therapeutic agents (e.g. corticosteroids) are permitted.

Prior therapy with convalescent plasma or anti-SARS-CoV-2 S protein targeted therapy are prohibited.

3.6.2. Concomitant Therapy

All therapies during the study should be recorded in the source document and eCRF.

Any medication including but not limited to over the counter or prescription medicines, vitamins, and/or herbal supplements, or other specific categories of interest must be recorded along with:

- Drug Name;
- Reason for use;
- Dates of administration including start and end dates;
- Dosage information including administration route, dose and frequency.

Any non-medication interventions must be recorded along with:

- Name of the interventions;
- Reason for use;

- Dates of intervention including start and end dates.

Any experimental treatment, anti-SARS-CoV-2 S protein targeted therapy and use of convalescent plasma are prohibited.

Currently, there are no data on the safety and efficacy of COVID-19 vaccine in persons who have been treated with anti-SARS-CoV-2 antibody. The anti-SARS-CoV-2 antibody like SCTA01 may interfere with the effectiveness of a COVID-19 vaccine. Considering the half-life of SCTA01, COVID-19 vaccination should not be administered for at least 120 days after the administration of SCTA01.

Best Supportive Care for Severe COVID-19:

Best supportive care (BSC) (including medications and non-medication interventions) for severe COVID-19 is allowed based on the local BSC policies or guidelines.

Medications for BSC may be constituted of but not limited to:

- Antiviral Therapy: Remdesivir®; others;
- Immune-Based Therapy: Dexamethasone; Prednisone; Methylprednisolone; Hydrocortisone; others;
- Adjunctive Therapy: Thrombolytic Therapy; others;
- Others.

Non-medication interventions for BSC may be constituted of but not limited to:

- Supplemental oxygen;
- High flow oxygen;
- Non-invasive ventilation;
- Invasive mechanical ventilation;
- ECMO;
- Others.

3.7. Replacement of Subjects

As the sample size determination is based on the number of patients required for the ITT analysis, patients who are randomly assigned and subsequently withdraw prior to completion of the study will not be replaced.

3.8. End of Study Definition

A participant is considered to have completed the study if he/she has completed all phases of the study including the last visit or the last scheduled procedure shown in the Table 4.

The end of the study is defined as the date of the last visit of the last participant in the study or last scheduled procedure shown in the Table 4 for the last participant in the trial globally.

4. SUBJECT ELIGIBILITY

4.1. Inclusion Criteria

1. Hospitalized patients with severe COVID-19 (5 point on the 8-point ordinal scale). According to the NIH definition, severe patients are those individuals who have one of the following: 1) respiratory rate > 30 breaths per minute; 2) $\text{SpO}_2 \leq 93\%$ on room air at sea level; 3) $\text{PaO}_2/\text{FiO}_2 < 300 \text{ mmHg}$ or $\text{SpO}_2/\text{FiO}_2 \leq 315 \text{ mmHg}$; 4) lung infiltrates $> 50\%$. In high altitude area (over 1000 meters), $\text{PaO}_2/\text{FiO}_2$ should be corrected according to the following formula: $\text{PaO}_2/\text{FiO}_2 \times [\text{760}/\text{barometric pressure (mmHg)}]^{30}$; 5 point: Hospitalized, requiring supplemental oxygen;
2. Subject (or authorized legal representative) has provided informed consent before any clinical activity related to the trial;
3. Subject (or authorized legal representative) understands and agrees to comply with the study procedures;
4. Male or female adult ≥ 18 years of age at the time of enrollment;
5. Has documented laboratory-confirmed SARS-CoV-2 infection as determined by polymerase chain reaction (PCR). Note: Patient can be enrolled before SARS-CoV-2 infection has been confirmed and can be tested by any approved clinical test other than PCR as long as SARS-CoV-2 infection is then confirmed by PCR;
6. ≤ 14 days since symptoms of COVID-19 onset;
7. Eligible COVID-19 vaccinated patients at the time of enrollment are allowed;
8. Women of childbearing potential (see Section 7.2.7) must agree to practice abstinence or use effective contraceptive methods with a failure rate of less than 1% per year during the study period; Male participants must agree to be abstinent from sexual intercourse or agree to use a male condom when engaging in any activity that allows for passage of ejaculate to another person during the study period.

4.2. Exclusion Criteria

1. Hospitalized patients who need non-invasive ventilation or high flow oxygen (i.e., 6 point on the 8-point ordinal scale);
2. Patients with critical COVID-19. According to the NIH definition, critical patients are those individuals who have one of the following: 1) respiratory failure and need invasive mechanical ventilation; 2) septic shock; 3) multiple organ dysfunction;
3. Patients with severe COVID-19 who received convalescent plasma or anti-SARS-CoV-2 S protein targeted therapy;
4. ALT or AST is 5 times higher than the upper limit normal range;
5. $\text{eGFR} < 30 \text{ mL/min}$ or on dialysis {eGFR calculated by Cockcroft-Gault formula (*Cockcroft DW, 1976*), Male: $\text{CrCL} (\text{mL/min}) = [(140 - \text{age}) \times \text{weight} (\text{kg})] \times 1/[\text{SCr}]$ }

(mg/dL) \times 72]; Female: CrCL (mL/min) = [(140 - age) \times weight (kg)] \times 0.85 / [SCr (mg/dL) \times 72] };

6. Pregnant or lactating women;
7. Anticipated discharge from the hospital or transfer to another hospital which is not a study site within 72 hours;
8. A patient who is allergic to the active ingredients or components of SCTA01;
9. Patients participated in other clinical studies related to COVID-19 or SARS-CoV-2 infection within 30 days before enrollment or five half-lives of investigational product, whichever is longer.

4.3. Screen Failures

Screen failures are defined as participants who consent to participate in the clinical study but are not subsequently randomly assigned to investigational product/entered in the study. A minimal set of screen failure information is required to ensure transparent reporting of screen failure participants, which includes demography, screen failure details, eligibility criteria, and any serious adverse event (SAE).

Individuals who do not meet the criteria for participation in this study (screen failure) may not be rescreened.

5. INVESTIGATIONAL PRODUCT MANAGEMENT AND ADMINISTRATION

5.1. Investigational Product

SCT will provide the investigators with the investigational product. SCTA01 will be provided as a sterile, liquid solution. Each glass vial contains 10 mL of study medication with a concentration of 25 mg/mL. The vial is designed for single use only and is not to be used to treat more than one subject. The supplied matching placebo is identical in physical appearance to that of the active injection and contains the same inactive ingredients which include histidine, sodium chloride, polysorbate 80, hydrochloric acid and injection grade water. They should be stored under refrigeration at 2~8°C (36-46°F) in the original carton to protect from light and avoid repeated freezing/thawing. Please refer to the Investigator Brochure for detailed investigational product information.

5.2. Administration

Each participant will receive a single intravenous infusion of either SCTA01 or placebo. Infusion volume will be 500 mL and infusion time is 3 hours (\pm 0 minutes).

Phase II part of the study: Subjects will receive a single dose of SCTA01 (15 mg/kg), SCTA01 (50 mg/kg), or placebo within 24 hours after randomization.

Phase III part of the study: Subjects will receive a single dose of SCTA01 (X mg/kg or X mg) or placebo within 24 hours after randomization.

Further instruction on the preparation and administration of the investigational product will be provided to the site in Pharmacy Manual.

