At the end of Phase II part, enrollment will be paused and the interim analysis for dose selection will be performed after the 285th subject has been observed for TTCI. An Independent Data Monitoring Committee (IDMC) will assess the benefit and risk to decide a dose for the Phase III part of the study.

Enrollment will be resumed after the IDMC has completed their evaluation and recommended the dose for the Phase III part.

The Phase III part will evaluate the efficacy, safety, and immunogenicity of SCTA01 at the dose recommended by the IDMC (X mg/kg or X mg) in hospitalized patients with severe COVID-19. The primary endpoint will evaluate the difference of TTCI between study group (SCTA01 X mg/kg or X mg + BSC) and control group (placebo + BSC) up to Day 29.

Approximately 510 subjects in Phase III part will be randomized by 1:1 ratio to SCTA01 (X mg/kg or X mg) group and placebo group, with 255 subjects in each group. IDMC will be used to monitor safety and efficacy of the study.

Total number of Phase II/III study is about 795.

Interim analysis (IA): There will be three un-blinded interim analyses when the 143rd patient in Phase II has completed Day 8 visit, at the end of Phase II and when the 160th patient in Phase III has completed Day 29 or Early Withdraw visit.

- The 1st interim analysis is for safety evaluation. The safety data will be reviewed at the 1st interim analysis, but the preliminary review of efficacy data is supported if early data and external emerging data warrants.
- The 2nd interim analysis is for dose selection: the analysis will be performed at the end of Phase II when the 285th patient completed Day 29 or Early Withdraw visit. The dose selected to continue to the Phase III part will be the dose with the greater effect in reduction of viral load compared to placebo at Day 8. Time to clinical improvement of each dose will be evaluated and the RR threshold of 1.15 will be used as a futility boundary at the end of Phase II. The futility boundary is non-binding, and the IDMC may recommend study continuation even if the futility bound is met on TTCI. If any safety signal is observed for any dose, the IDMC will weigh this information against the efficacy results in selecting the dose for Phase III.

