1.2. Secondary Objectives

- To evaluate the clinical efficacy of SCTA01 as assessed by clinical severity, hospitalization, mortality (Phase II, III);
- To evaluate the safety of SCTA01 (Phase II, III);
- To evaluate the virologic efficacy of SCTA01 (Phase II, III);
- To evaluate the pharmacokinetics of SCTA01 (Phase II);
- To evaluate the immunogenicity of SCTA01 (Phase II, III).

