- The 1st interim analysis is for safety evaluation. Only safety data will be reviewed at the 1st interim analysis. The IDMC may request to review efficacy data if early data warrants. Decision s from the IDMC will take the nature of premature data into account unless prevailing data suggest conclusive outcome of the trial. Early safety signal will guide patient enrollment to maximize the effectiveness of treating this patient population with SCTA01.
- The 2nd interim analysis is for dose selection: the analysis will be performed at the end of Phase II when the 285th patient completed Day 29 or Early Withdraw visit. The dose selected to continue to the Phase III part will be the dose with the greater effect in reduction of viral load compared to placebo at Day 8. Time to clinical improvement of each dose will be evaluated and the RR threshold of 1.15 will be used as a futility boundary at the end of Phase II. The futility boundary is non-binding, and the IDMC may recommend study continuation

even if the futility bound is met on TTCI. If any safety signal is observed for any dose, the IDMC will weigh this information against the efficacy results in selecting the dose for Phase III.

- The 3rd interim analysis is the penultimate analysis that allows for stopping for superior efficacy. It is planned when 160 patients in Phase III (approximately 31% information time of Phase III part, which will have approximately 128 TTCI events) have been documented in the ITT population. If the interim analysis is performed at 31% of information time of Phase III, based on Pocock type boundary of α -spending function, a 1-sided p -value less than 0.01068 using inverse normal method to combine p -value from Phase II part and Phase III part will need to be observed to declare statistical significance. A futility boundary of an observed RR of 1.22 will be used to declare failure of the study when TTCI events from Phase II and Phase III part combined are exactly 280, which is equivalent to an observed one-sided p -value of 0.05.

Note: The critical values of nominal p -value and hazard ratio that will be used to declare statistical significance and/or futility at the interim analysis will be calculated based on the actual number of the TTCI events documented at the time the interim analysis.

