9.3. Statistical Decision Rules

A combined *p*-value using inverse normal method of less than 1-side of 0.01068 from 3rd interim analysis or less than 1-side of 0.0166 from final analysis will need to be observed to declare statistical significance. The total number of patients in the ITT analysis sets for primary analysis will include patients in the recommended dose group in Phase II and in the same dose group that continued in Phase III, or the control group. i.e., 95 + 255 = 350 patients for recommended dose group or for control group. The patients from the inferior dose group (95 patients) in Phase II will only contribute to the multiplicity penalty of dose selection.

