9.7.2. Multiple Testing in Adaptive Seamless Design

9.7.2.1 Combination Test

Confirmatory testing of the hypothesis comparing optimal dose with placebo using data collected from Phase II and Phase III part will use a closed testing procedure. This hypothesis will be rejected at level α (one-side 0.025) if it and all intersection hypotheses involving it are all rejected at local level α (one-side 0.025). The testing strategy used to combine results from Phase II and Phase III part will be a combination test based on the inverse normal weighting method, with the test statistic of the combination test calculated as (*Bauer and Kohne 1994*):

$$\text{Sqrt}(n_1/n)*\Phi^{-1}(1-p_1) + \text{Sqrt}(n_2/n)*\Phi^{-1}(1-p_2)$$

Where n_1 and n_2 are the sample size in Phase II and III, respectively, $n = n_1+n_2$, Φ refers to the standard normal distribution, and p_1 and p_2 are the p -value from Phase II and III, respectively. p_1 is the Simes-adjusted p -value in Phase II, and p_2 is the unadjusted p -value to compare optimal dose with placebo in Phase III.

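### Phase III may use an X mg regimen that is neither Phase II arm, but the only success rule combines the two phases as one dose; these passages must be reconciled

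*Combined protocol and SAP*

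**What the plan says.** Section 5.2 describes Phase II as "Subjects will receive a single dose of SCTA01 (15 mg/kg), SCTA01 (50 mg/kg), or placebo within 24 hours after randomization". For Phase III the same section says "Subjects will receive a single dose of SCTA01 (X mg/kg or X mg) or placebo within 24 hours after randomization". The Synopsis repeats the option, "at the dose recommended by the IDMC (X mg/kg or X mg) in hospitalized patients with severe COVID-19", and it also stands in Sections 2.10, 3.1 and 5.6. It is therefore a consistent feature of the text, not a single slip.

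The selection rule in Section 3.1 chooses between the doses studied: "The dose selected to continue to the Phase III part will be the dose with the greater effect in reduction of viral load". It gives no step from a mg/kg dose to a flat one.

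Section 9.3 defines the primary analysis population as "patients in the recommended dose group in Phase II and in the same dose group that continued in Phase III", together with the control group, 95 + 255 = 350 per group. Success is a combined p-value "less than 1-side of 0.01068 from 3rd interim analysis or less than 1-side of 0.0166 from final analysis". Section 9.7.2.1 describes "Confirmatory testing of the hypothesis comparing optimal dose with placebo using data collected from Phase II and Phase III part", with p1 (Simes-adjusted) from Phase II and p2 (unadjusted) from Phase III joined by the inverse normal method. Section 9.7.6 repeats the combined rule for the final analysis.

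I found no rule in the text for converting a mg/kg dose to a flat dose, no exposure-matching condition, and no test for the case in which the Phase III regimen is not a Phase II arm.

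**The concern.** A closed combination test supports a claim about a given dose only if both stages test that dose. If Phase III used a flat dose, p1 would compare a mg/kg regimen with placebo and p2 would compare a different regimen with placebo. Rejection would mean that at least one of the two null hypotheses is false. It would not say which, although the Phase III regimen is the one a reader would take the claim to be about. The 350-per-group analysis would also average over two regimens.

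Section 9.7.2.2 promises control at one-sided 0.025 of the chance of rejecting any true null hypothesis. The null hypothesis for a flat regimen is not among those tested in Phase II, so that promise does not cover it.

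**Working it through.** **Inputs.**
- Table 7 and Section 9.7.6: 149 events at the end of Phase II, 280 at the third interim, 556 at the end. Phase III therefore contributes 280 - 149 = 131 and 556 - 149 = 407. The 80% event rate gives nearly the same: 0.8 x 160 = 128 and 0.8 x 510 = 408.
- Thresholds 0.01068 and 0.0166 (Section 9.3); design RR 1.4 (Section 9.4).
- Squared weight of Phase II: 285/795 = 0.358 from total phase sizes, or 190/700 = 0.271 if only the two analysed arms count. Section 9.7.2.1 can be read either way.

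**The plan's own figures.** Pocock-type spending on Phase III information gives 0.025 x ln(1 + (e - 1) x 0.31) = 0.01068, as stated. The matching final boundary is 0.01666 at t = 0.31 and 0.0166 at t = 128/408. Power at RR 1.4 by the Schoenfeld formula (556 events, one-sided 0.0166) is 96.7%, so the claim of over 90% reproduces.

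**How much Phase II can carry.** At the final analysis the test rejects when

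sqrt(w) x z(p1) + sqrt(1 - w) x z(p2) > z(0.0166) = 2.130.

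With w = 0.358 and p1 = 0.01, z(p2) must exceed (2.130 - 0.5987 x 2.326)/0.801 = 0.92. That is p2 up to 0.179, an observed Phase III RR of about exp(0.92 x 2/sqrt(407)) = 1.10. Likewise:

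| Phase II p1 | Largest p2 that succeeds, w = 0.358 | w = 0.271 |
|---|---|---|
| 0.01 | 0.179 | 0.141 |
| 0.001 | 0.364 | 0.271 |
| 0.0001 | 0.548 | 0.411 |

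**False success if the Phase III regimen is inactive (RR 1.0).** Normal-approximation simulation, at least 1,000,000 runs per case. Each log-rank statistic has mean ln(RR) x sqrt(events/4); the two Phase II comparisons share the placebo group; the full closed test is applied at both looks. The plan selects on Day 8 viral load, whose relation to time to clinical improvement (TTCI) is not given, so two extremes were run: selection unrelated to TTCI, and the better TTCI result carried forward. Figures are without futility stopping.

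| Phase II RR | Dose carried forward | w = 0.358 | w = 0.271 |
|---|---|---|---|
| both 1.4 | unrelated to TTCI | 21.4% | 17.5% |
| both 1.4 | better TTCI | 26.8% | 21.7% |
| one 1.4, one 1.0 | better TTCI | 19.2% | 15.7% |
| both 1.2 | unrelated to TTCI | about 8% | about 7% |
| both 1.2 | better TTCI | 10.5% | 9.0% |

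Following both futility bounds (RR 1.15 and 1.22) lowers these by roughly 1 to 2 percentage points; for example, 21.4% becomes 19.7% and 15.7% becomes 14.8%. Phase III alone against the same boundaries gives 2.5% in every row.

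**If no regimen works.** The combined test rejects in about 1.6% of trials (w = 0.358, selection unrelated to TTCI), and in 1.5-2.2% when the better TTCI result is carried forward. That is within 2.5%.

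**Power at RR 1.4 in both phases, no futility stopping.** Combined test 96.2%; Phase III alone, same two boundaries, 90.3%.

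**The case against.** The best defence is that X mg is a placeholder. The selection rule picks one of the two Phase II doses and Section 9.3 requires the same dose to continue, so a flat dose, if used, would merely express the selected mg/kg dose. That is a fair reading of the intent. It does not settle the matter, because a flat dose and a mg/kg dose coincide at only one body weight. Set to match at an assumed 80 kg, a flat dose is 80/50 = 160% of the mg/kg dose at 50 kg and 80/120 = 67% at 120 kg. The text sets no condition on how close the two must be.

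The defence is also right that the large figures need a mg/kg dose that works and a flat dose that does nothing. Section 2.9 itself suggests that efficacy may not depend on dose. An inactive flat regimen is a worst case, not a forecast.

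Three stronger readings are tempting and are not supported:
- A reader might infer that success could be declared for an untested regimen. Any Phase III regimen would be randomised against placebo, 255 versus 255, with 64-73% of the squared weight. The fault is borrowed Phase II evidence, not absence of testing.
- A reader might infer, from pharmacokinetics being an objective in Phase II only ("To evaluate the pharmacokinetics of SCTA01 (Phase II"), that the regimens could not be bridged. Sections 7.6 and 9.10 foresee population modelling with covariates and outside data, and weight is recorded on Day 1. A Phase II model could predict flat-dose exposure. What is missing is a requirement to do so before combining.
- A reader might count the higher rejection rate for a weakly active Phase III regimen as error. If that regimen has any true benefit, rejecting is correct; the difference is power.

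Finally, the protocol defers some detail to an SAP and to the IDMC Charter. The absence of a rule can be asserted only for the text available here.

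**Conclusion.** The point holds as a conflict between passages with a conditional consequence. The design, administration and randomisation text permits a Phase III regimen that the analysis text assumes cannot occur. Under that option, following the written success rule can give a wrong confirmatory conclusion about the Phase III regimen.

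The size depends on facts not yet known. There is no error if the two regimens behave alike, and error is controlled if none works. With an inactive Phase III regimen, false success is about 7-10% at Phase II RR 1.2 and about 15-27% at RR 1.4, depending on the weights, on how selection relates to TTCI, and on whether one or both doses work. With only one working dose, the lower end assumes that selection tends to carry it forward; if the inactive dose were chosen, the figure would be lower. All figures assume proportional hazards and the planned event counts. If Phase III uses one of the two mg/kg arms, the point falls away.

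**What to change.** Reconcile the Synopsis and Sections 2.10, 3.1, 5.2 and 5.6 with Sections 9.3 and 9.7.2.1. Which regimen Phase III should use is for the sponsor.

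Before the end-of-Phase II unblinding, add to 9.3 and 9.7.2.1: *The inverse normal combination and the pooled 350-per-group analysis apply only if the Phase III regimen is the same as a Phase II arm. Otherwise the confirmatory test uses the Phase III p-value alone against the same boundaries (0.01068 at the third interim, 0.0166 at the final analysis), and Phase II is supportive.* The event triggers for that case would be stated as Phase III counts (131 and 407), with boundaries recalculated from actual events as the plan already provides. The timing matters because a choice of test made after Phase II results are seen would be data-driven.

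The cost is a sentence or two, plus some power if the regimen does change. At RR 1.4 power falls from about 96% to about 90%, so the chance of missing a true effect rises from about 4% to about 10%. That is still about the stated figure. The rule would also set Phase II aside for a flat dose well matched in exposure. If the regimen does not change, nothing is lost.
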